1. LIST OF ABBREVIATIONS

Ab	Antibody
ACR	Albumin to Creatinine Ratio
AE	Adverse Event
AER	Albumin Excretion Rate
ALP	Alkaline Phosphatase
ALT	Alanine Amino Transferase
AST	Aspartate Amino Transferase
ATC	Anatomical Therapeutic Chemical
BAFF	B Cell Activating Factor
BMI	Body Mass Index
bpm	Beats per Minute
CGI	Clinical Global Impression
CI	Confidence Interval
CIDP	Chronic Inflammatory Demyelinating Polyradiculoneuropathy
CRA	Clinical Research Associate
CRF	Case Report Form
CRO	Contract Research Organization
CNTN1	Contactin 1
DILI	Drug-induced Liver Injury
dps	Decimal Places
EOS	End of Study
FAS	Full Analysis Set
FC γ R	FC-gamma Receptors
GFR	Glomerular Filtration Rate
γ GT	γ Glutamyl Transferase
Hb	Hemoglobin
HBe	Hepatitis B core Antigen
HBs Ag	Hepatitis B surface Antigen
HCV	Hepatitis C Virus
HIV	Human Immunodeficiency Virus
ICH	International Conference on Harmonization
Ig	Immunoglobulin
IgA	Immunoglobulin A
IgG	Immunoglobulin G
IMP	Investigational Medicinal Product
INCAT	Inflammatory Neuropathy Course and Treatment

IVIG(g)	Intravenous Immunoglobulin
KM	Kaplan-Meier
kPa	Kilopascal (Pressure Unit)
LDH	Lactate Dehydrogenase
LFT	Liver Function Test
LLN	Lower Limit of Normal
LOCF	Last Observation Carry Forward
LOESS	Local Polynomial Regression
MCV	Mean Corpuscular Volume
MDRD	Modified Diet in Renal Disease
MedDRA	Medical Dictionary for Regulatory Activities
MRC	Medical Research Council
NF155	Neurofascin 155
PCR	Protein to Creatinine Ratio
PER	Protein Excretion Rate
PPS	Per Protocol Set
PT	Preferred Term
R-ODS	Rasch-built Overall Disability Scale
SAE	Serious Adverse Event
SAP	Statistical Analysis Plan
SAS	Statistical Analysis System
SCIG(g)	Subcutaneous Immunoglobulin
SI	Standard International
SMQ	Standardized MedDRA Query
SOC	System Organ Class
SOP	Standard Operating Procedure
SWI	Standard Working Instruction
TAAE	Temporarily Associated Adverse Event
TEAE	Treatment Emergent Adverse Event
TTS	Total Treated Set
ULN	Upper Limit of Normal
USG	Ultrasonography
WHO	World Health Organisation

2. INTRODUCTION

2.1. Study Objectives

2.1.1. Primary objective

The primary objective of this study is to assess the efficacy of I10E in improving the disability of patients with chronic inflammatory demyelinating polyradiculoneuropathy (CIDP).

2.1.2. Secondary objectives

The secondary objective of this study is to assess the safety of I10E in patients with CIDP.

The secondary objectives also include the following exploratory objectives:

- To assess a potential relationship between serum total IgG trough levels, biomarkers levels and clinical response - as assessed by neurological scales - in patients with CIDP.
- To assess a potential relationship between ultrasonography (USG) coupled to neurophysiology analysis of nerves and clinical response - as assessed by neurological scales - in patients with CIDP (ancillary study in Italy).

2.2. Study Design

This study is a phase III, international, multicentre, single-arm, open-label, prospective study.

2.3. Sample Size

The study is designed to demonstrate superiority of I10E to an historical control in terms of responder rate. The historical responder rate with placebo is estimated from the ICE study ([Hughes RA 2008](#)). As a conservative estimate the upper boundary of the 95% confidence interval (CI) of the observed rate is used (observed rate $12/58 = 20.7\%$, 95% CI [11.2%, 33.3%]). Based on this historical placebo responder rate of 33.3% and a 60% responder rate with I10E, 38 evaluable patients are needed in order to obtain 90% power using an exact binomial test with a one-sided nominal level of significance $\alpha=2.5\%$. Presuming 10% non-evaluable patients, 42 patients will be included in the study (around one third of all patients will be either Immunoglobulin [Ig]-naïve or relapsing Ig-pre-treated).

2.4. Investigational Schedule and Randomisation

Depending on the version of protocol, the total duration of the study for a patient is approximately 24-27 weeks or 24-29 weeks. Each patient is screened during a maximum of 15 days or 4 weeks. The duration of treatment is approximately 21 weeks. A follow-up period of 3 weeks +/- 7 days will take place after the administration of the last study drug. At the end of the follow-up period, patients will undergo an EOS visit.

Randomisation is not applicable in this single-arm study.

2.5. Evaluation Criteria

2.5.1. Primary efficacy criterion

The primary efficacy criterion is response rate at the End-of-Study visit (EOS). Response is defined as a decrease ≥ 1 point in the adjusted inflammatory neuropathy course and treatment (INCAT) disability score between baseline and the EOS visit.

2.5.2. Secondary efficacy criterion

The secondary efficacy endpoints are the following:

- Response rate at 12 weeks
- Time to response
- Rate of patient with no change in CIDP treatment at 12 weeks and EOS visit
- Changes from baseline to 12 weeks and EOS visit in the following scores:
 - Adjusted INCAT disability score
 - Grip strength with the Martin vigorimeter in both hands
 - Rasch-built Overall Disability Scale (R-ODS)
 - Patient and Investigator Clinical Global Impression (CGI)
 - Medical Research Council (MRC) 12 muscles sum score (0 to 5)
 - Rasch-modified MRC sum score (0 to 3).

2.5.3. Safety criteria

The safety criteria include:

- Treatment emergent adverse events (TEAEs)
- Serious adverse events (SAEs)
- Temporarily associated adverse events (TAAEs), i.e., AEs that begin during an infusion or within 72 hours after an infusion
- Clinically significant changes from baseline in vital signs
- Clinically significant changes from baseline in laboratory parameters

2.5.4. Exploratory criteria

Biomarker study

- Anti-Contactin 1 (CNTN1) and anti-Neurofascin 155 (NF155) antibodies titers at screening and EOS visit
- Fc γ receptor IIB (Fc γ RIIB) B cells marker levels at visits V2, V3 and V4
- B-cell activating factor (BAFF) at visits V2, V3, V4 and EOS visit
- Complement components (C3 and C4 antigens, CH50) at visits V2, V3, V4 and EOS visit
- Serum total IgG trough levels at each visit, within 24 hours prior to study drug administration

2.6. Study Plan Table

	Screening	First study drug administration	Day 4 after last infusion at V2	Week 3	Week 6	Week 9	Week 12	Week 15	Week 18	Week 21	End of study visit
	VISIT 1	VISIT 2	VISIT 3	VISIT 4	VISIT 5	VISIT 6	VISIT 7	VISIT 8	VISIT 9	VISIT 10	VISIT 11
Informed consent (before any procedure of study)	X										
Inclusion/exclusion criteria verification	X	X									
Demographics & Medical history	X										
Safety											
Adverse events assessment	X	X	X	X	X	X	X	X	X	X	X
Phone call 4 days (+/- 1 day) after study drug administration				X	X	X	X	X	X	X	
Concomitant medications	X	X	X	X	X	X	X	X	X	X	X
Patient diary (delivery and verification)	X	X	X	X	X	X	X	X	X	X	X
Clinical assessments / Before study drug administration											
Complete physical examination	X	X	X								X
Clinical examination focused on arterial or venous thromboembolic signs				X	X	X	X	X	X	X	
Weight, Body temperature, heart rate, arterial blood pressure (systolic and diastolic)	X	X	X	X	X	X	X	X	X	X	X
Efficacy assessments / Before study drug administration											
INCAT disability score	X	X		X	X	X	X	X	X	X	X
MRC sum-score, Rash modified MRC sum-score R-ODS Grip Strength (both hands)		X					X				X
Patient and Investigator: CGI (Severity)		X					X				X
Patient and Investigator: CGI (Efficacy), CGI (Improvement)							X				X

Biological test Local lab / Before study drug administration	VISIT 1	VISIT 2	VISIT 3	VISIT 4	VISIT 5	VISIT 6	VISIT 7	VISIT 8	VISIT 9	VISIT 10	VISIT 11
Serum Total IgG trough levels		X		X	X	X	X	X	X	X	X
HbA1c (only for patients with a known history of diabetes mellitus), serum IgA levels	X										
Urine protein reagent strip test	X ^a		X ^b	X ^b	X ^b	X ^b	X ^b	X ^b	X ^b	X ^b	X ^b
Urine Pregnancy test for female of child bearing potential	X										X
C3 and C4 antigens		X	X	X							X
Anti HBs & anti HBc Ab, HBs Ag tests, HIV and HCV tests	X										X
Complete blood count and differentials, Hemoglobin, Mean corpuscular volume, platelet count, haptoglobin, LDH	X		X	X	X	X	X	X	X	X	X
Reticulocytes, direct Coombs test, total serum protein level	X										X
AST, ALT, γ GT, ALP	X										X
Creatininemia, GFR ^c , total and free bilirubin ^d	X		X	X	X	X	X	X	X	X	X
Serum reference sample for long term storage		X									X
Biological test Local lab in case of suspected clinical thrombosis											
D-Dimers		X	X	X	X	X	X	X	X	X	X
Biological test Local lab in case of suspected hemolysis											
Reticulocytes, direct Coombs test		X	X	X	X	X	X	X	X	X	X
Exploratory assessment Central lab / Before study drug administration											
anti-CNTN1 and anti-NF155 antibodies	X										X
BAFF, CH50		X	X	X							X
Fc γ R1IB (on B cells)		X	X	X							
Ultrasonography coupled to neurophysiology (Italian sites only)	X										X
Study drug administration											
I10E - 2g/kg		X									
I10E - 1g/kg				X	X	X	X	X	X	X	
Vital signs 30-45 minutes and 60-75 minutes after the start of study drug administration (each day of study drug administration)											
Body temperature, Heart rate, Arterial blood pressure (systolic and diastolic)		X		X	X	X	X	X	X	X	
Vital signs 30-45 minutes after the end of study drug administration (each day of study drug administration)											
Body temperature, Heart rate, Arterial blood pressure (systolic and diastolic)		X		X	X	X	X	X	X	X	

^a To be done in all patients. See below for actions dependent on urine protein reagent strip result at screening:

Urine protein reagent strip test result	Action
Negative or Trace	No further urine test required
1 cross (1 +)	Verify eligibility after either assessing AER or PER from a 24h-urine collection sampled before the first study drug course, or assessing ACR or PCR from a spot urine sample immediately following the urine protein reagent strip test (i.e. urine obtained before study drug administration).
2 crosses (2 +) or more	Patient should be excluded

^b To be performed before study drug administration in patients who at screening tested for urine protein reagent strip result "1 cross 1 (+) and/or had GFR_c in the range of 60-80 mL/min/1.73m²:

Urine protein reagent strip test result	Action
Negative or Trace	No further urine test required
1 cross (1 +) or more	Assess either AER or PER from a 24h-urine collection sampled at least 7 days after the end of the previous study drug course or assess ACR or PCR from a spot urine sample immediately following the urine protein reagent strip test (i.e. urine obtained before study drug administration). At all visits except End of Study visit: The Investigator must review these results in time prior to the next study drug administration and consider if any of the Early Discontinuation Criteria / Stopping Rules (see Section 5.4 of the protocol) apply.

^c According to modification of diet in renal disease (MDRD) calculation

^d Total bilirubin in all patients; if total bilirubin > ULN, free bilirubin will be assessed from the same blood sample, as total bilirubin

3. GENERAL STATISTICAL CONSIDERATIONS

3.1. Description of Variables

Continuous data will be described using number of valid observations, number of missing observations, mean, standard deviation, median, quartiles, minimum and maximum.

Categorical data will be described using number of missing observations, number of valid observations per category and percentage. Number of missing observations will not be taken into account for the calculation of percentages.

For descriptive statistics, the following number of decimal places (dps) will generally be applied:

- 3 dps for values in [0, 0.9995)
- 2 dps for values in [0.9995, 9.995)
- 1 dp for values in [9.995, 99.95)
- 0 dp for values ≥ 99.95

For negative values the same rule will be followed using the absolute value.

For original case report form (CRF) variables the minimum and maximum will use the same number of dps as the raw data. Statistics on count variables (e.g. number of infusions) will generally be presented with 1 dp while the minimum and maximum will be presented without dp. Percentages will be presented with 1 dp. Exceptions from these rules might be applied when necessary.

3.2. Handling of Missing Data and Outliers

Regarding the primary criterion, a patient will be also considered as a non-responder if the patient is withdrawn due to lack of efficacy of the treatment (insufficient response to the investigational medicinal product [IMP]). In all other cases, if the INCAT score at EOS visit is missing, then the Last Observation Carried Forward (LOCF) approach will be applied and the last available adjusted INCAT disability score will replace the missing value at EOS visit.

The LOCF approach will also be used to handle the missing data of the secondary endpoint for adjusted INCAT and response at week 12 only.

When AEs are documented in the diary, dates of AE onset may be missing and as a result, TAAE cannot be defined. For AEs with a missing or incomplete start date, the response to the question “Did the AE start within 72 hours of an infusion” will be used for determining if the AE is temporally related to the infusion.

Partial dates of first symptoms and partial dates of diagnosis will be imputed by 15 if only the day is unknown and by 1st July if day and month are unknown. No imputation will be done if the year is unknown.

For the calculation of duration of AEs, partial start and end dates will be imputed with the first and last possible date within the period defined by the partial date, respectively. In general, no

calculation of duration will be made if either the start date or stop date is missing, i.e., cannot be imputed using pre-determined rules. No other general rules for the replacement of missing data are planned.

Data listings will always show the original CRF reported values and not the imputed values.

3.3. Handling of Local Laboratory Data

Local laboratory data will first be standardized. Standardization is the process of converting original local laboratory results to agreed standard international (SI) units. This process allows laboratory parameters to be presented in the same measurement units across the study.

Given that local laboratories are utilized for the study, normalization of the laboratory results will be performed ([Karvanen 2003](#)). Normalization is the process of transforming results from different local laboratories in such a way that the results are directly comparable. For normalization the parameter lower and upper limits from a local laboratory (S_{Lo}, S_{Up} - see Section [5.7.6. 1](#)) provided by Clinical Research Physician are chosen to represent a standard laboratory. The standardized reported result (R_S) and the local lower and upper limits for given parameter (I_{Lo}, I_{Up}) are then placed into an expression, of which the now normalized result (R_N) may be treated as if it was obtained from a central laboratory.

$$\text{Either } R_N = S_{Lo} + \left(\frac{R_N - I_{Lo}}{I_{Up} - I_{Lo}} \right) \times (S_{Up} - S_{Lo}) \text{ known as location-scale formula}$$
$$\text{Or } R_N = R_S \times \left(\frac{I_{Lo}}{S_{Lo}} \right) \text{ known as the scale formula}$$

Note that standardization (i.e., unit conversion to SI unit) will be done prior to normalization; this allows the laboratory results to be converted to the same measurements prior to being transformed so that results can be directly comparable.

The normalized result will be used for descriptive summaries; displays of laboratory categories such as abnormalities and shifts from baseline based on Low (below lower limit of normal [LLN]), Normal (between LLN and upper limit of normal [ULN]) and High (above ULN) classifications and displays for observed and change values. When normalization of a parameter is not possible (e.g. estimated Glomerular Filtration Rate), then the untransformed standardized result will be presented.

Normalizations will be performed using the ranges provided in Section [5.7.6. 1](#).

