5.7.6. Reference tables for derivations

5.7.6. 1. Reference ranges for local laboratory normalization

The following ranges have been reviewed and agreed by LFB Clinical Research Physician of the study:

Table 5–1: Reference ranges for normalization of local laboratory data

Laboratory test			Reference Ranges		Formula
Test name	Short name	Standard Units	Lower Limit of Normal (LLN): S_{Lo}	Upper Limit of Normal (ULN): S_{Up}	
Alanine Aminotransferase	ALT	IU/L	5	35	location-scale
Alkaline Phosphatase	ALP	IU/L	42	141	location-scale
Aspartate Aminotransferase	AST	IU/L	8	30	location-scale
Bilirubin	BILI	$\mu\text{mol/L}$	3	17	location-scale
Bilirubin, Free	BILIF	mg/dL	0,2	0,8	location-scale
Creatinine	CREAT	$\mu\text{mol/L}$	44	106	location-scale
D-Dimer	DDIMER	ug/L	0	500	location-scale
Ery. Mean Corpuscular Volume	MCV	fL	79	96	location-scale
Erythrocytes	RBC	$10^{12}/\text{L}$	4	5	location-scale
Gamma Glutamyl Transferase	GGT	IU/L	8	35	location-scale
Glomerular Filtration Rate	GFR	$\text{mL}/\text{min}/1.73\text{m}^2$	60	.	scale
Haptoglobin	HAPTOG	mg/dL	40	200	location-scale
Hematocrit	HCT	%	36	48	location-scale
Hemoglobin	HGB	g/dL	12	16	location-scale
Hemoglobin A1C	HBA1C	mmol/mol	20	42	location-scale
Lactate Dehydrogenase	LDH	IU/L	250	450	location-scale
Leukocytes	WBC	$10^9/\text{L}$	4	10	location-scale
Platelets	PLAT	$10^9/\text{L}$	150	450	location-scale
Protein	PROT	g/dL	6	8	location-scale
Protein Excretion Rate	PROTEXR	mg/day	0	100	location-scale

5.7.6. 2. Normative values for grip strength

Normative values ([Merkies 2000](#)) for quantitative grip strength assessment with the Martin vigorimeter for both hands in healthy subjects (kPa) are presented in [Table 5–2](#):

Table 5–2: Normative values for grip strength

Age (year)	Median values (KPa) per age span and gender	
	Males	Females
15-19	122	90
20-24	146	106
25-29	154	112
30-34	153	109
35-39	148	104
40-44	141	104
45-49	134	98
50-54	126	92
55-59	116	84
60-64	105	76
65-69	97	71
70-74	91	67
75-79	82	63
80-84	75	59
≥85	64	54

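### SAP 3.3 prints the scale formula for laboratory normalisation with its ratio inverted; the error reaches GFR only, and only if Table 5-1 is followed over the SAP 3.3 exception

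*SAP*

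**What the plan says.** SAP section 3.3 first converts local results to common units, giving R_S, and then normalises them. One set of limits, S_Lo and S_Up, "are chosen to represent a standard laboratory". I_Lo and I_Up are "the local lower and upper limits for given parameter". The output R_N "may be treated as if it was obtained from a central laboratory".

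Two expressions follow:

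- R_N = S_Lo + ((R_N − I_Lo) / (I_Up − I_Lo)) × (S_Up − S_Lo), "known as location-scale formula"
- R_N = R_S × (I_Lo / S_Lo), "known as the scale formula"

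The normalised result feeds the descriptive summaries and the "displays of laboratory categories such as abnormalities and shifts from baseline based on Low", Normal and High classes.

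On GFR the SAP says two things. Section 3.3 states: "When normalization of a parameter is not possible (e.g. estimated Glomerular Filtration Rate), then the untransformed standardized result will be presented". Table 5-1 in section 5.7.6.1 nevertheless has a row for "Glomerular Filtration Rate" with lower limit 60 mL/min/1.73m², no upper limit, and *scale* in the formula column. It is the only one of the 20 tests with that entry; the other 19 use location-scale.

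**The concern.** Normalisation should carry a site's reference limit onto the standard reference limit, so that a result at the edge of normal locally is at the edge of normal on the common scale. A formula that does not do this moves results to the wrong place relative to the cut-point that then classifies them.

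If the printed scale formula were programmed for GFR, the by-visit summaries, the abnormality counts and the shift tables for renal function could be wrong at any site whose lower limit is not 60. The protocol lists acute renal failure among the important potential risks (section 9.2.1), so these tables should be right.

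**Working it through.** The SAP gives no worked normalisation example, so there is no figure to reproduce. The check is whether each formula maps the local limit to the standard limit.

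**Inputs.** S_Lo = 60 for GFR (Table 5-1). The roles of R_S, I and S are from SAP 3.3. Classification uses the standardised ranges (SAP 4.7.3.1). Site GFR limits are not in the documents; I_Lo = 50, 60, 75, 80 and 90 are assumptions chosen to show the range.

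**Anchor check.** Put R_S = I_Lo. The printed formula gives I_Lo × I_Lo / S_Lo = I_Lo² / 60, which equals 60 only when I_Lo = 60. The reversed ratio gives I_Lo × 60 / I_Lo = 60 for every site.

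**Cut-point under the printed formula.** A result is classed Normal when R_S × I_Lo / 60 ≥ 60, that is, when R_S ≥ 3600 / I_Lo. Untransformed, it is Normal when R_S ≥ 60.

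| Assumed I_Lo | Printed formula maps I_Lo to | Printed: Normal from | Class change versus untransformed |
|---|---|---|---|
| 50 | 2500/60 = 41.7 | 3600/50 = 72 | 60 to <72: Normal becomes Low |
| 60 | 3600/60 = 60.0 | 60 | none |
| 75 | 5625/60 = 93.8 | 3600/75 = 48 | 48 to <60: Low becomes Normal |
| 80 | 6400/60 = 106.7 | 3600/80 = 45 | 45 to <60: Low becomes Normal |
| 90 | 8100/60 = 135.0 | 3600/90 = 40 | 40 to <60: Low becomes Normal |

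**Single values.**

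- I_Lo = 90, GFR 50: printed 50 × 90/60 = 75.0 (Normal); reversed ratio 50 × 60/90 = 33.3 (Low); untransformed Low.
- I_Lo = 90, GFR 39: printed 58.5. It is raised but stays Low.
- I_Lo = 75, GFR 50: printed 62.5 (Normal); reversed ratio 40 (Low); untransformed Low.
- I_Lo = 50, GFR 65: printed 54.2 (Low); reversed ratio 78.0 (Normal); untransformed Normal.

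**Corrected ratio versus no transformation.** These two are not equivalent. At I_Lo = 90, GFR 75 becomes 75 × 60/90 = 50 (Low) with the corrected ratio, but is Normal untransformed. The first keeps the site's own classification; the second classifies everyone against 60. The SAP therefore has to settle which applies before the formula is corrected.

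**Location-scale formula.** With R_S in the numerator it passes the anchor check: for ALT (standard 5 to 35) and assumed local limits 10 to 50, a result of 10 maps to 5 and 50 maps to 35. As printed, R_N stands on both sides and the patient's result never enters. For haemoglobin (standard 12 to 16) with assumed local limits 13 to 17.5, let k = (16 − 12)/(17.5 − 13) = 0.889. Solving gives R_N = (12 − 13k)/(1 − k) = 0.444/0.111 = 4.0 for every patient.

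**The case against.** The strongest reply is that section 3.3 itself names estimated GFR as a parameter shown untransformed. No other test in Table 5-1 uses the scale formula, so if that sentence governs, the inverted ratio touches nothing. This stands, and it is why the point is conditional. It does not remove the error. Section 3.3 closes by directing normalisation to the ranges in section 5.7.6.1, where GFR is marked *scale*. Section 4.7.3.1 names only haematology differential counts as an exception to normalised values and then lists GFR among the parameters to be summarised. A programmer working from the table would apply the printed formula.

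A second reply is that GFR is not the only view of the kidney. Creatinine is summarised separately and uses location-scale; all laboratory abnormalities are to be listed; clinically significant laboratory findings are adverse events; and acute renal failure is a defined query among the other significant adverse events. This also stands, and it limits the exposure to the GFR displays.

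A third reply is that the repeated R_N is an obvious slip, or an error in reading the equation from the PDF, since the text defines R_S as the quantity entered. That is fair: 4.0 for every patient shows that the printed line is unusable, and is not a forecast of what would be programmed. A swap of whole symbols between numerator and denominator in the scale formula is less likely to be a reading error, but checking the source file settles both. The SAP also plans a statistical validation plan and output review, which may catch these slips but would be checking against a specification that is itself wrong.

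**Conclusion.** The scale formula is wrong as printed. Its effect is conditional on GFR being normalised as Table 5-1 indicates, and on a site limit other than 60. The class changes tabulated above rest on assumed site limits, so the number of patients affected cannot be stated. The reach is confined to descriptive GFR summaries, abnormality counts and shift tables. No efficacy analysis uses these values.

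A reader might infer that any GFR below a site's own lower limit would be raised and classed as Normal, so that impaired renal function is hidden in the safety tables. The documents do not support that. Section 3.3 says GFR is untransformed. Even if it is normalised, a site-low result becomes Normal only when the site limit exceeds 60 and the result is at least 3600/I_Lo; lower results stay Low, and for site limits below 60 the error runs the other way. Nor does a GFR of 75 at a site with a limit of 90 illustrate hidden impairment: 75 is above the SAP's standard limit of 60 and is Normal untransformed.

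**What to change.** 1. Decide whether GFR is normalised, and make SAP 3.3 and Table 5-1 agree.
2. If GFR stays untransformed, delete the scale formula and the *scale* entry for GFR, since no other test uses it. If it is normalised, print R_N = R_S × (S_Lo / I_Lo).
3. In the location-scale formula, which serves the other 19 tests, replace R_N by R_S on the right-hand side, after checking the source SAP for a transcription artefact.
4. Check the normalisation program against the corrected text, including a test that each local limit maps to its standard limit.

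The cost is a few lines in the SAP and one program check. No new data and no change to any efficacy analysis are needed.

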4.7.3. Other safety endpoints

4.7.3. 1. Laboratory data

Quantitative descriptions of laboratory data will be performed on normalized values as outlined in Section 3.3 with the exception of hematology differential counts for which standardized values will be used because values collected as a ratio of WBC count cannot be normalized into a range in absolute unit. For these parameters results expressed in percentages of WBC will be converted to absolute count by multiplying WBC count by the value collected in percentage (ranges will not be transformed).

4.7.3. 1.1. Patient level analyses

All laboratory values will be reported in SI units. Summary displays for laboratory safety data (hematology and chemistry) will be produced by visit for both observed and change from baseline values of the different laboratory analyses. Laboratory tests taken only at screening, those in case of a qualifying event (e.g., thrombosis or hemolysis), and urine protein reagent strip test results will be presented in the laboratory listings. The following clinical parameters will be summarized:

- Hematology:
 - Complete blood count + differentials, hemoglobin (Hb), mean corpuscular volume (MCV), platelet counts
 - Haptoglobin
- Biochemistry:
 - Creatinemia, glomerular filtration rate according to MDRD
 - LDH
 - Total and free bilirubin (total bilirubin in all patients; if total bilirubin > ULN, free bilirubin will be assessed from the same blood sample, as total bilirubin)
 - AST, ALT, alkaline phosphatase (ALP), γ GT
 - Total serum protein level
 - Serum IgA levels

Laboratory values will be classified as normal, low, or high based on standardized normal ranges. Laboratory categories will be expressed in terms of the L (below lower limit of normal [LLN]), N (between LLN and ULN) and H (above ULN) classifications for numerical measurements and normal, abnormal for categorical measurements. The number and percentage of patients with abnormal values will be summarized for each laboratory parameter by visit. These summaries will include the number and percentage of patients with “any pre-treatment visit” and “any on-treatment visit post baseline” abnormality for each parameter. These displays will ensure that all abnormal values will be captured.

LNH shifts in clinical laboratory values (hematology and chemistry) from baseline to each visit post first dosing will be summarized by visit. Patients with values outside the normal range will be flagged.

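### SAP 3.3 says estimated GFR is shown untransformed, but SAP Table 5–1 gives GFR, and no other test, the scale normalisation

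*SAP*

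**What the plan says.** SAP 3.3 sets two steps for local laboratory results. The first is a unit conversion: "Standardization is the process of converting original local laboratory results to agreed standard international (SI) units". The second, normalisation, moves each converted result onto the range of one chosen reference laboratory, by either a location-scale or a scale formula. The normalised result then feeds the summaries, abnormality displays and shifts. The section makes one exception: "When normalization of a parameter is not possible (e.g. estimated Glomerular Filtration Rate), then the untransformed standardized result will be presented". It then says "Normalizations will be performed using the ranges provided in Section" 5.7.6.1.

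That section holds Table 5–1, which has 20 rows. Nineteen carry the location-scale formula. The row "Glomerular Filtration Rate" has a lower limit of 60 mL/min/1.73m², no upper limit, and the scale formula.

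SAP 4.7.3.1 includes MDRD GFR among the summarised parameters and says "Quantitative descriptions of laboratory data will be performed on normalized values as outlined in Section 3.3". The only exception it names itself is haematology differential counts, for which "ranges will not be transformed". On flags it says: "Laboratory values will be classified as normal, low, or high based on standardized normal ranges".

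**The concern.** The one parameter that 3.3 names as not normalisable is the one parameter to which Table 5–1 gives its own normalisation formula. If 3.3 governs, the scale formula is used for nothing. If the table governs, the example in 3.3 is wrong. Two programmers could each follow the SAP and deliver different GFR summaries, changes from baseline, Low/Normal counts and shift tables.

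A second, smaller gap follows. If GFR stays untransformed, the SAP does not say outright which lower limit flags it: the tabulated 60 or each laboratory's own limit. It gives a range rule for differential counts and none for GFR.

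Values close to the cut-off are to be expected. The protocol's study plan and section 8.2.3 single out patients with a screening GFR of 60–80 for repeat urine testing, and protocol 9.2.1 lists acute renal failure among the important potential risks.

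**Working it through.** The SAP states no figure to reproduce here. The check compares the two rules and then illustrates how far apart they can be.

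**Inputs.** Reference lower limit S_Lo = 60 (Table 5–1). Local lower limit I_Lo: not given anywhere, so 50, 60, 75 and 90 are assumed. Measured GFR falling from 70 to 55: chosen for illustration.

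**Rule A (SAP 3.3).** The value shown is R_S, the result after unit conversion only.

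**Rule B (Table 5–1).** The value shown is R_S × (S_Lo / I_Lo). This orientation is used because it carries a result at the local limit to the reference limit: I_Lo × 60 / I_Lo = 60. The factors are 60/50 = 1.2, 60/60 = 1, 60/75 = 0.8 and 60/90 = 0.667.

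| Assumed local limit | Rule A, flagged at 60 | Rule A, flagged at local limit | Rule B, flagged at 60 |
|---|---|---|---|
| 50 | 70 to 55: Normal to Low | 70 to 55: Normal to Normal | 84 to 66: Normal to Normal |
| 60 | 70 to 55: Normal to Low | 70 to 55: Normal to Low | 70 to 55: Normal to Low |
| 75 | 70 to 55: Normal to Low | 70 to 55: Low to Low | 56 to 44: Low to Low |
| 90 | 70 to 55: Normal to Low | 70 to 55: Low to Low | 46.7 to 36.7: Low to Low |

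**Size of the change.** The measured fall is 15. Under Rule B it is reported as 15 × 1.2 = 18 at a local limit of 50, 15 × 0.8 = 12 at 75, and 15 × 0.667 = 10 at 90.

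**Where the flags part.** R_S × 60 / I_Lo is below 60 exactly when R_S is below I_Lo. Rule B flagged at 60 therefore gives the same flags as Rule A flagged at the local limit, and both can differ from Rule A flagged at 60. The band of disagreement is 50 to below 60 at a local limit of 50, 60 to below 75 at 75, and 60 to below 90 at 90. The last band contains the whole 60–80 range.

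**Why this matters for GFR and not for other tests.** With R_S as the input, the location-scale formula puts a result below S_Lo exactly when R_S is below I_Lo, and likewise at the upper limit. Each value judged against its own range gets the same flag, so an imprecise statement of which range applies does no harm there. An untransformed GFR has no such protection.

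**The formulas in 3.3.** In the available text the scale ratio reads I_Lo / S_Lo. So oriented, a result at the local limit becomes I_Lo² / 60, which is 41.7 at 50 and 135 at 90, instead of 60. The location-scale numerator reads R_N, although the prose names the input as "The standardized reported result (R_S) and the local lower and upper limits for given parameter". Either may be a fault of the PDF text, and the table above relies on neither. The conflict holds in either orientation, because each changes GFR unless the local limit is 60.

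**The case against.** The best reply is that the SAP has a workable order of precedence. Section 3.3 is explicit and names the parameter, and 4.7.3.1 refers back to it, so untransformed GFR is the more natural reading. That has force, and the fix follows it. It does not settle the matter: 4.7.3.1 excepts only differential counts in its own words, and the table entry is just as explicit. One can also imagine a conditional rule, with scaling where a laboratory supplies a lower limit and no transformation where it does not. The SAP nowhere states that rule, and 3.3 gives GFR itself as the example.

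On the flagging limit, the objection largely succeeds. Section 3.3 describes the reference limits as those of a standard laboratory, so the phrase in 4.7.3.1 can be taken to mean Table 5–1. The table prints only one GFR limit, 60, and the protocol uses the same figure in its renal exclusion criterion. A reader might infer that flagging is undefined. The documents support less: 60 is a natural reading that is not stated.

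A reader might also infer that a clearly low GFR would be displayed as normal. With the ratio as it reads in the text, a measured 55 at an assumed local limit of 90 becomes 55 × 90 / 60 = 82.5. That figure depends on an orientation that may be a text-extraction fault, so it is not part of the finding. With the ratio the other way, 55 at that limit is Low under every reading.

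Finally, every local limit used here is assumed. If all sites use 60, nothing changes.

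**Conclusion.** The point holds as a minor internal inconsistency: SAP 3.3 and Table 5–1 give incompatible instructions for GFR. No stated figure in the plan is wrong. Whether outputs differ depends on local lower limits, which the documents do not give. At 60 the rules agree; away from 60 they give different values and can give different flags and shifts. The number of sites or patients affected cannot be estimated from the documents.

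The consequence is limited to descriptive GFR displays. Creatinine is summarised separately, acute renal failure is a prespecified MedDRA query, and SAP 4.7.3.1.2 lists all abnormalities. The primary endpoint does not use laboratory data, and eligibility is decided on GFR at screening, outside these displays. The documents do not support any inference that the efficacy conclusion or patient selection is at risk. Nor is it established that the formulas in 3.3 are misprinted; that needs a look at the original page.

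**What to change.** Reconcile the two places. The simplest way, in line with 3.3, is to replace the scale entry in the GFR row of Table 5–1 with a note that GFR is not normalised, keeping the lower limit of 60. Then add a sentence to SAP 4.7.3.1 saying that GFR is summarised untransformed and flagged at all sites against one limit; the tabulated 60 is the only GFR reference limit the SAP prints. The opposite repair, dropping the GFR example from 3.3 and keeping a correctly oriented scale formula, would also remove the conflict. It would need a local lower limit from every laboratory.

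Separately, check both formulas in 3.3 against the original page. The location-scale numerator should use R_S. If the scale formula is printed with the local limit over the reference limit, correct it to R_S × (S_Lo / I_Lo), or remove it if no test uses it.

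The cost is a few lines of SAP text, with no effect on patients or data collection. SAP 5.3 speaks of v2.0 as already past, so programs may exist; if they do, confirm which GFR rule and which limit they apply.
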